4.4 Technical Implementation

The LLM system (GPT-OSS) is operated locally on servers at the Klinikum rechts der Isar (on-premise). No data are transmitted to external servers or cloud services. The system is not classified as a medical device and is used solely to support text simplification, not for diagnosis or treatment decisions.

5 Criteria for Early Study Termination

Individual Discontinuation:

- Withdrawal of consent by the participant
- Subsequent identification of an exclusion criterion

Termination of the Entire Study:

- Decision by the principal investigators for scientific or organizational reasons
- Request by the responsible ethics committee or supervisory authority
- Unexpected, serious safety concerns

6 Study Population

6.1 Inclusion Criteria

- Age 18 years or older
- Inpatients of the Department of Medicine III (Hematology/Oncology) at TUM University Hospital
- Receipt of a discharge letter including the sections Current Status, Medical History, Epicrisis, and Further Management as part of routine clinical care
- Capacity to provide informed consent
- Written informed consent following the consent procedure

Additional Inclusion Criteria for the Translation Arm:

- Insufficient German language proficiency
- Native language supported by the LLM system (English, Turkish, Arabic, Russian, Polish, Spanish, Italian, French, Portuguese, Vietnamese, Chinese)

6.2 Exclusion Criteria

- Cognitive impairments that preclude independent assessment of comprehension (e.g., dementia, severe encephalopathy)
- Participation in another study with potential influence on the endpoints
- Lack of capacity to provide informed consent
- Refusal to participate in the study

6.3 Patient Recruitment

Recruitment proceeds consecutively during inpatient ward rounds in the Department of Medicine III. Potential participants are identified by the treating medical staff. No recruitment materials such as flyers or notices are used.

7 Data Protection and Data Security

7.1 Informed Consent

Study participation requires prior written informed consent. The consent procedure is conducted by a study physician. Participants are given a reflection period of at least 24 hours. Consent may be withdrawn at any time without giving reasons and without any disadvantage to further treatment.

7.2 Legal Basis

The legal basis for processing personal data is informed consent pursuant to Art. 6(1)(a) and Art. 9(2)(a) GDPR in conjunction with § 27 BDSG.

7.3 Data Collection and Storage

Data collected include: demographic data (age, sex, educational level, native language), clinical baseline data (diagnosis, treatment setting), questionnaire data, and interview data where applicable. All study data are pseudonymized (study code oncOPAL-XXXX) and stored in a password-protected electronic database on servers of the Klinikum rechts der Isar. Data transmission is encrypted (TLS 1.3).

7.4 Pseudonymization

Each participant is assigned a unique alphanumeric study code. The mapping list is stored separately from the study data in an encrypted document. Access is restricted to the principal investigator and a designated deputy. All analyses are performed exclusively with pseudonymized data.

7.5 Data Disclosure

Personal data are not disclosed to third parties. Publications use exclusively aggregated, anonymized data. Transfer of data to non-EU countries is not planned.

7.6 Withdrawal and Data Deletion

In the event of withdrawal, no further data are collected. Already collected data may be deleted upon request, provided they have not yet been incorporated into the analysis in anonymized form. After expiry of the retention period (10 years), all study data will be fully deleted and the mapping list destroyed.

7.7 Access Control

Access to study data is protected by individual user accounts with strong passwords and is logged. Servers are located in a secured data center with access control.

8 Benefit-Risk Assessment

The benefit-risk ratio is favorable. Participants in the intervention group and translation arm receive an additional plain-language synopsis that can promote understanding of diagnosis and treatment. Study participation involves minimal burden (additional time requirement of approximately 5–15 minutes). There are no physical risks. Psychological risks are low; the risk of possible misunderstandings arising from the simplified presentation is mitigated by mandatory physician review. Routine clinical care remains completely unchanged.

9 Sample Size and Power Analysis

The sample size calculation is based on the following assumptions: a clinically relevant difference in the primary endpoint of 1.5 points, an expected standard deviation of 2.5 points, power of 80%, significance level $\alpha = 0.05$ (two-sided), a randomization ratio of 2:1, and an expected dropout rate of 10%.

For a two-sided t-test for independent samples, the required sample size is $n = 136$ (91 intervention, 45 control). Accounting for the dropout rate, $n = 150$ patients will be recruited for the randomized part.

For the translation arm, $n = 30$ patients will be enrolled. This sample size permits a descriptive evaluation of feasibility without a formal statistical comparison.

10 Funding

The study is funded through internal resources of the Institute for Diagnostic and Interventional Radiology and the Department of Medicine III at TUM University Hospital (Klinikum rechts der Isar). There are no conflicts of interest.

11 References

1. Kessels RPC. Patients' memory for medical information. J R Soc Med. 2003;96(5):219-222.
2. Jeblick K, et al. ChatGPT Makes Medicine Easy to Swallow: An Exploratory Case Study on Simplified Radiology Reports. Radiology. 2024;308(1):e230618.

3. Ayers JW, et al. Comparing Physician and Artificial Intelligence Chatbot Responses to Patient Questions Posted to a Public Social Media Forum. *JAMA Intern Med.* 2023;183(6):589-596.
4. Arraras JL, et al. The EORTC QLQ-INFO25: A questionnaire to assess information given to cancer patients. *Eur J Cancer.* 2010;46(15):2726-2738.
5. Basch E, et al. Overall Survival Results of a Trial Assessing Patient-Reported Outcomes for Symptom Monitoring During Routine Cancer Treatment. *JAMA.* 2017;318(2):197-198.

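### Section 9's n = 136 is not the 80%-power size for its own inputs: they require about 102 evaluable patients, and 91 + 45 gives about 90% power

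*Protocol*

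**What the plan says.** Section 9 (Sample Size and Power Analysis) of the protocol lists its inputs together: "a clinically relevant difference in the primary endpoint of 1.5 points", "an expected standard deviation of 2.5 points", 80% power, a two-sided 5% significance level, "a randomization ratio of 2:1" and 10% dropout. It names the test, "For a two-sided t-test for independent samples", and gives the result: "the required sample size is $n = 136$ (91 intervention, 45 control"). Dropout is applied only after that: "Accounting for the dropout rate, $n = 150$ patients will be recruited for the randomized part". The synopsis splits the 150 into 100 intervention and 50 control. No other allowance is stated, whether for a rank test, multiplicity or covariates.

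**The concern.** The section gives every input that the calculation needs, so its result can be checked directly. A standardised difference of 1.5/2.5 = 0.6 is moderately large, and 136 evaluable patients is well above what 80% power needs at that effect, even with 2:1 allocation.

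At stake is whether the justification for the trial's size can be relied on. If the power label is wrong, the protocol misdescribes its own design. If the size is wrong, 136 is called a requirement when it is not one, and anyone judging a recruitment shortfall against it would use the wrong threshold. If an unstated SD or difference lies behind the 136, then a planning assumption is misreported.

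**Working it through.** **Inputs (all from Section 9).** Difference 1.5; SD 2.5; standardised effect d = 1.5/2.5 = 0.6; two-sided alpha 0.05; power 80%; 2:1 allocation; independent-samples t-test; dropout 10%.

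**1. Attempt to reproduce the stated 136, normal approximation.**
n(control) = (1 + 1/2) × (1.960 + 0.842)² / 0.6² = 32.7, rounded up to 33. Total = 66 + 33 = 99. The stated 136 is not reproduced.

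**2. Exact t-test (noncentral t).**
Noncentrality = 0.6 / √(1/n₁ + 1/n₂), with n₁ + n₂ − 2 degrees of freedom.

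| Intervention + control | Total | Power |
|---|---|---|
| 66 + 33 | 99 | 79.6% |
| 68 + 34 | 102 | 80.8% |
| 90 + 45 | 135 | 90.4% |
| 91 + 45 (stated) | 136 | 90.5% |
| 100 + 50 (all randomised evaluable) | 150 | 93.1% |

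The smallest exact 2:1 size reaching 80% is 102. The stated size is 136 − 102 = 34 patients higher, and 34/102 = 33%.

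**3. Dropout.** 102/0.9 = 113.3, so 114 recruited. Section 9 applies dropout after the 136, so dropout cannot explain the gap.

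**4. Could another convention give 136 at 80% power?**
- One-sided test: 78 (normal) to 81 (exact t).
- Two-sided alpha 0.025: 120. Alpha 0.01: 147 (both normal approximation).
- Mann-Whitney test, which the synopsis names as the alternative: 105 at relative efficiency 0.955, 117 at the worst case of 0.864.
- 1:1 allocation: 88 (normal) or 45 per arm (exact t, power 80.4%).

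None gives 136. Among the two-sided variants tried, only 90% power comes close: 135 (90 + 45) by exact t, 132 by normal approximation.

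**5. What would make 91 + 45 an 80% design?** Solving the exact power equation for one input at a time gives an SD of about 2.92 with the difference kept at 1.5, or a difference of about 1.29 with the SD kept at 2.5. Neither value appears in the protocol.

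**The case against.** The best defence is that nothing is lost. At the stated inputs the planned numbers give more power than claimed. The type I error, endpoint, allocation and effect estimate are untouched. No termination criterion in Section 5 refers to 136, and Section 8 describes the burden on participants as minimal. This stands, and it makes the point a reporting correction rather than a threat to the trial's conclusions. It does not make the printed figure right.

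Three stronger readings are tempting, and the protocol does not support them.

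- **A second error in the dropout step.** A reader might note that 136/0.9 = 151.1 and that 150 less 10% leaves 135. But Section 9 does not say how dropout is applied, and 136 × 1.10 = 149.6, which rounds to 150. The difference between the two conventions is one or two patients.
- **A 90% calculation labelled as 80%.** This fits well, since 135/0.9 = 150, but only after replacing the printed 136 (91 + 45) with 135 (90 + 45). Other origins are possible: 45 is also the per-arm size for a 1:1 design at 80% power, with the intervention arm then roughly doubled, or a different SD or difference may have been used. The document does not show which, so relabelling the power as 90% cannot be taken as the correction without the sponsor's confirmation.
- **An unconditional 90% power.** The figure holds for a test of zero difference when the true difference is 1.5 and the SD is 2.5. Section 3.4 words the null hypothesis to include differences below 1.5. Against that null, a true difference of 1.5 lies on the boundary, and neither 80% nor 90% applies. Section 9 describes an ordinary two-sided t-test, so the check here follows Section 9.

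**Conclusion.** Wrong as written; should be fixed. For the inputs in Section 9, 80% power needs about 102 evaluable patients (99 by normal approximation), or about 114 recruited with 10% dropout, not 136. The stated 136 gives about 90.5% power, some 10 points above the stated 80%. At least one of the stated power, the stated size and the stated inputs must therefore be wrong, and the protocol does not show which.

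The trial is not underpowered at its stated inputs. The conclusion assumes a common SD of 2.5, a true difference of 1.5 and a test against zero. The gap is far larger than the 3 patients that separate the normal approximation from the exact t-test.

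**What to change.** Keep 150 randomised (100 + 50). Rewrite the Section 9 paragraph so that inputs, power and size agree, and state which was intended:

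- (a) if 90% power was intended, state 90% with about 135 evaluable (90 + 45);
- (b) if 80% was intended, give the required size as 102 (68 + 34), say that 150 is recruited by choice, and report the power this provides: about 90% at 135 evaluable;
- (c) if 136 came from a different SD or difference, state that input.

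In each case add that the power refers to a test of zero difference, and say how the 10% dropout allowance was applied. The cost is one corrected paragraph, with no extra patients and no design change.
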